2.3. Study Design

Overview of Study Design and Key Features	

Design Features
	
 • Part 1 Dose Escalation 
 ○ Population: Subjects with relapsed/refractory MM (originally planned to enrol up to 30 subjects. However, additional subjects were enrolled to explore a new intermediate dose group) ○ Objective: characterize safety, PK, PD, immunogenicity and establish RP2 dose of GSK2857916 ○ Two dosing schedules (Schedule 1 and Schedule 2) may be explored: 
 ▪ Schedule 1: GSK2587916 once every 3 weeks (21-day cycle) (n~20) ▪ Schedule 2: GSK2587916 once weekly for 3 consecutive weeks, 1-week rest (28-day cycle) (n~9). Schedule 2 was not actually explored. ○ Serial PK samples will be collected from all subjects in Part 1 • Part 2 Expansion Cohort(s) (n~50 subjects) 
 ○ Population: 
 ▪ Subjects with relapsed/refractory MM (up to 40 subjects) ▪ Subjects with lymphomas expressing BCMA (up to 10 subjects) ○ Objective: Further evaluate the safety, PK, immunogenicity, and clinical activity of GSK2857916 at the RP2 dose identified in Part 1 ○ MM and Lymphoma expansion cohorts will be analyzed separately ○ Sparse PK samples will be collected from all subjects • Genetics research samples will be collected predose from all subjects

Overview of Study Design and Key Features	
Dosing	
 • Part 1 Dose Escalation Initially, GSK2857916 will be administered (IV) via 60 min infusion once every three weeks (21 days = 1 cycle) on Schedule 1. Once an MTD1 or RP2D has been established on the once every 21-day (Schedule 1), the safety, tolerability, PK, and PD of once-weekly dosing (Schedule 2) of GSK2857916 may be explored as an additional cohort(s). • Part 2: Dose Expansion Phase Subjects enrolled in Part 2 dose expansion phase will be administered GSK2857916 at recommended phase 2 dose (RP2D) established based on Part 1 outcomes.
Time & Events	
 • Refer to Appendix 2: Schedule of Activities
Treatment Assignment	
 • This is a non-randomized open-label study.
Interim Analysis	
 • Part 1: Dose Escalation Phase No formal interim analysis is planned for Part 1. Safety, pharmacokinetic and pharmacodynamic marker data will be examined on an ongoing basis to support dose escalation decisions. • Part 2: Dose Expansion Phase 
 ○ For MM cohort, one futility analysis based on ORR data was performed after approximately 30 subjects are evaluable (originally 3 futility analyses are planned after approximately 15, 22 and 30 subjects are evaluable). The number of confirmed responses (PR or better) observed will be compared with the stopping rules provided in Section 13.6.2 of the protocol. ○ For the lymphomas expressing BCMA cohort, no interim analyses will be performed, though consideration would be given to closing the cohort should the enrolment be stopped in the MM cohort.

2.4. Statistical Hypotheses / Statistical Analyses

No formal statistical hypotheses will be tested in Part 1. Analysis of the data obtained from Part 1 will only utilize descriptive methods. In Part1, dose escalation/de-escalation decisions will be informed by the Bayesian approach: N-CRM (Neuenschwander-Continuous Reassessment Method) [[Neuenschwander, 2008](#)]. Details of the N-CRM model used for this study is described in Section [3.1.1](#).

The assumption for ORR in part 2 MM cohort is:

The null hypothesis H_0 : $ORR \leq 20\%$

The alternative hypothesis H_A : $ORR \geq 40\%$.

No hypothesis testing is planned for part 2 MM cohort. The methodology utilized is based on the predictive probability of success if enrollment continues to 40 subjects [[Lee, 2008](#)]. The predictive probability design is similar to a Green-Dahlberg design in that it allows for early stopping for futility. The differences are that the predictive probability design allows for evaluation of stopping rules as often as after each subject, rather than at only two stages. While the two designs have similar type I and type II error rates, the

probability of early termination is greater with the predictive probability design. In this particular study, one futility analysis based on ORR data was performed after approximately 30 subjects are evaluable (originally 3 futility analyses are planned after approximately 15, 22 and 30 subjects are evaluable).

3. PLANNED ANALYSES

3.1. Interim Analyses

3.1.1. Part 1: Dose Escalation Phase

While no formal interim analysis is planned for Part 1, safety, pharmacokinetic and pharmacodynamic marker data will be examined on an ongoing basis to support dose escalation decisions. Prior to determining the GSK2857916 dose for the next cohort enrolled, exploratory analysis will be conducted to assess the relationship of GSK2857916 dose levels with safety, PK and PD parameters using all data from available cohorts.

Dose escalation/de-escalations decisions will take into account all available data, including but not limited to the safety parameters, PD and PK data of all cohorts assessed. Dose escalation/de-escalation decisions will be informed by the N-CRM (Neuenschwander-Continuous Reassessment Method) [Neuenschwander, 2008]. The N-CRM model used for Schedule 1 is described in detail in Section 3.1.1.1 and Section 3.1.1.2. The method is fully adaptive and makes use of all DLT information available at the time of each dose assignment.

3.1.1.1. Description of the New Continual Reassessment Method

The N-CRM is a type of Bayesian adaptive dose-escalation scheme that estimates the parameters of a statistical model relating dose and toxicity, and is expected to locate the MTD efficiently while minimizing the number of subjects exposed to pharmacologically inactive or unsafe dose levels. The method is fully adaptive and makes use of all the toxicity information available at the time of each dose assignment. N-CRM estimates may be provided at dose escalation meetings as supportive material to the primary 3+3 dose escalation design.

The N-CRM estimates, for each potential dose, the (Bayesian) posterior probabilities that the DLT rate lies in each of four predefined toxicity ranges:

- A dose falls in the **Under-dosing** range if the rate of a DLT at the dose is in the interval [0%, 16%).
- A dose falls in the **Target** toxicity range if the rate of a DLT at the dose is in the interval [16%, 33%).
- A dose falls in the **Excessive** toxicity range if the rate of a DLT at the dose is in the interval [33%, 60%).

- A dose falls in the **Unacceptable** toxicity range if the rate of a DLT at the dose is in the interval [60%, 100%].

Additionally, the following over-dose constraints for the recommended dose will be maintained:

- The posterior probability of the DLT rate lying in the Excessive Toxicity or Unacceptable Toxicity range is 0.25 or less.
- The recommended dose is no more than 2 times that of the previous dose.
- Note that a de-escalation recommendation is possible using this method. At the time of each dose-escalation decision, the dose with the highest posterior probability of lying in the Target Toxicity range (subject to the given constraints) will be the model-recommended dose for the next cohort.

The N-CRM procedure for Schedule 1 will utilize a single subject/cohort run-in phase.

The single subject (small cohort) run-in will be halted when the first \geq Grade 2 toxicity for which relationship to the investigational agent cannot be ruled out occurs in one subject in Cycle 1 (21 days). At this point, the cohort will be expanded to 3 or more subjects at the same dose level and the escalation will continue to follow the N-CRM procedure as outlined in [Table 2](#)

Table 2 Single Subject (Small Cohort) Run-In Procedure for GSK2857916 given on Schedule 1 (once every 21 days)

Dose Level	Number of subjects with \geq G2 toxicity	Dose Escalation/Action
Dose Level 1/Cohort 1	0 out of 1 subject (Sentinel subject)	Predicted starting dose 0.03 mg/kg every 21 days
Dose Level 2/Cohort 2	0 out of 1 subject	Escalate to the next dose level with increase \leq 100% of the starting dose
Dose Level 3 and beyond/Cohort 3 and beyond	0 out of 1 subject	Escalate to the next dose level with increase of \leq 100% of the dose tested in the previous cohort
	1 out of 1 subject*	Switch to Cohort size of 3 or more subjects

*Increase of doses **up to** 100% of the previous dose may continue until the first \geq Grade 2 toxicity for which relationship to the investigational agent cannot be ruled out occurs in one subject in Cycle 1 (21 days). At this point the single subject (small cohort) run-in is halted. Continue with N-CRM, with cohort sizes of 3 or more subjects. Increase of doses \leq 100% will be considered for subsequent cohorts of 3 or more subjects.

3.1.1.2. Prior Probability Distribution

Elicited prior probabilities of a DLT at each dose were used to determine the prior distribution of the parameters of an explicit logistic dose-toxicity model, namely

$$\ln\left(\frac{p_d}{(1-p_d)}\right) = \alpha + \beta * \ln\left(\frac{d}{d_m}\right),$$

where p_d is the probability of a DLT at dose d , and d_m is a reference dose.

The prior distribution of $(\alpha, \ln(\beta))$ will be assumed to be bivariate normal with means (standard deviations): $E[\alpha]=-1.3281$ (1.7153), $E[\ln(\beta)]=-0.795$ (1), with correlation between α and $\ln(\beta)$ set to $\rho=-0.9352$ and $d_m=0.72$ mg/kg.

3.1.1.3. Displays To Be Created For Dose Escalation Review

Review of preliminary data will be performed after completion of each dosing cohort in Part 1. Preliminary safety and study population data may include a demographic summary, adverse event (AE) summary, AE summary by maximum toxicity category, SAE listing, listing of AEs that are reported to be DLT's, and listing of AEs leading to dose modification. Spreadsheets containing relevant study data may also be supplied by the study data manager.

Further, after single subject run-in was halted, after each expanded cohort in dose escalation, the recommended dose from the N-CRM method and updated posterior estimates of the probabilities of being in each dose-toxicity range may be provided. The Fixed and Adaptive Clinical Trial Simulator (FACTS) (Version 2.4 or higher) software from Tessella will be used to make N-CRM calculations.

Prior to determining a dose for the next cohort, exploratory analyses will be conducted to assess the relationship of dose levels with safety, PK, and pharmacodynamic parameters using all data from available cohorts.

The GSK study team, in collaboration with study investigators, will review all relevant data to support:

- whether the current dose had acceptable toxicity, and
- the decision regarding the next dose level based on the totality of the data

3.1.2. Part 2 Expansion Phase

3.1.2.1. Multiple Myeloma Expansion Cohort

During Part 2 (Expansion Cohort), futility analyses of response data will be conducted in order to determine whether the futility criteria for stopping have been met. The study will not be stopped early for efficacy, but is designed to stop early for futility if the predictive probability of success is less than 5%.

For Multiple Myeloma cohort, response data will be reviewed once approximately 30 subjects are evaluable at the RP2D dose and the number of confirmed responses (PR, VGPR, CR, and sCR) will be compared with the stopping rules provided in [Table 3](#) based on predictive probability design of Lee et al. [[Lee, 2008](#)].

In addition to considering the recommendations of the futility analyses, final decisions on stopping enrolment in the MM cohort will depend on the totality of the data collected. Should the recommendation to stop for futility be disregarded in favour of a decision to continue the trial based on the totality of the data, the overall type I error rate of the expansion phase will be inflated.

Table 3 Futility Stopping Region for Multiple Myeloma Expansion Cohort

Number of Evaluable Subjects	Number of Overall Responses												
	0	1	2	3	4	5	6	7	8	9	10	11	>11
15													
16													
17													
18													
19													
20													
21													
22													
23													
24													
25													
26													
27													
28													
29													
30													
31													
32													
33													
34													
35													
36													
37													
38													
39													
40													

3.1.2.1.1. Operating Characteristics of the Stopping Rules for Futility

The stopping rule in [Table 3](#) is based on the methodology of Lee et al. [[Lee, 2008](#)]. For the MM expansion cohort, starting with 15 subjects and allowing for a maximum sample size of 40, this design will have a type I error rate of 0.075 and 89.8% power. Under the null hypothesis, if the true response rate is 20%, the expected sample size of the design is 23.4 subjects and probability of early termination (PET) is 88.9%. Under the alternative hypothesis, if the true response rate is 40%, the expected sample size of the design is 38.6 subjects and probability of early termination (PET) is 8.5%.

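### The futility operating characteristics in SAP section 3.1.2.1.1 describe monitoring after every subject from 15, not the single look at about 30 that the plan uses

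*SAP*

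**What the plan says.** Section 3.1.2.1 sets the rule. The cohort is "designed to stop early for futility if the predictive probability of success is less than 5" per cent, there is no early stop for efficacy, and "response data will be reviewed once approximately 30 subjects are evaluable at the RP2D dose", when the number of confirmed responses is compared with Table 3.

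Section 2.4 says that "one futility analysis based on ORR data was performed after approximately 30 subjects are evaluable", where looks at about 15, 22 and 30 had been planned originally. Section 2.3 says the same.

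Section 3.1.2.1.1 then gives the properties of the stopping rule. For a design "starting with 15 subjects and allowing for a maximum sample size of 40", it says "this design will have a type I error rate of 0.075 and 89.8% power". At a true response rate of 20% it gives an expected sample size of 23.4 and a probability of early termination (PET) of 88.9%. At 40% it gives 38.6 and 8.5%.

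Section 2.4 also compares methods in general terms, saying that the "probability of early termination is greater with the predictive probability design" than with a Green-Dahlberg design.

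**The concern.** The look schedule was updated and the operating characteristics were not. Section 3.1.2.1.1 is in the present tense, and nothing labels its figures as those of a superseded schedule. A reader would take them as the properties of the futility analysis described one section earlier.

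What is at stake is the stated chance of stopping early with a drug that has a 20% response rate, and the number of subjects expected to be enrolled in that case. Both look much more favourable than a single late look can deliver. The stated type I error is also somewhat too low.

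**Working it through.** **Inputs from the SAP.** Response rates of 20% (null) and 40% (alternative), maximum sample size 40, first look at 15 for the stated figures, and stopping if the predictive probability of success is below 5% (sections 2.4, 3.1.2.1 and 3.1.2.1.1).

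**Assumptions.** Success means at least 12 responses in 40, and the prior is Beta(0.2, 0.8). The SAP text gives neither, although Table 3 or the protocol may.

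**Check without assumptions.** Write E(N) = PET × (mean N among stopped trials) + (1 − PET) × 40. The stated null figures imply a mean N at stopping of (23.4 − 0.111 × 40) / 0.889 = 18.96 / 0.889 = 21.3. The alternative figures imply (38.6 − 0.915 × 40) / 0.085 = 2.0 / 0.085 = 23.5. Neither is possible if the first chance to stop comes at about 30. Even with PET at 88.9%, a single look at 30 would give E(N) = 40 − 10 × 0.889 = 31.1.

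**Reproducing the stated figures.** An exact binomial recursion, dropping paths whenever the predictive probability is below 0.05, gives:

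| Schedule | Type I error | Power | PET at 20% | E(N) at 20% | PET at 40% | E(N) at 40% |
|---|---|---|---|---|---|---|
| Stated in 3.1.2.1.1 | 0.075 | 89.8% | 88.9% | 23.4 | 8.5% | 38.6 |
| After every subject, 15 to 39 | 0.0754 | 89.75% | 88.85% | 23.42 | 8.49% | 38.64 |
| 15, 22 and 30 | 0.080 | 90.8% | 68.3% | 25.7 | 4.6% | 39.0 |
| Once, at exactly 30 | 0.086 | 92.7% | 60.7% | 33.9 | 1.7% | 39.8 |

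The second row agrees with the first on all six figures, to within 0.1 percentage point or 0.1 subject. With the same prior and a look after every subject, success cut-offs of 11 or 13 in 40 do not agree: type I error is about 0.14 and 0.037. The three-look row depends on the prior. With Beta(1, 1) it becomes 0.085, PET 62.4% and E(N) 29.8 at 20%, which is also far from the stated set.

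**Single look at 30, step by step.**
- Boundary: after 6 of 30, success needs at least 6 of the last 10. The predictive probability is 0.016 to 0.022 across seven priors tried, so the trial stops. After 7 of 30, success needs at least 5 of 10, and the probability is 0.086 to 0.106, so it continues. The boundary of 6 or fewer does not depend on the choice among these priors.
- PET = P(X₃₀ ≤ 6): 0.607 at 20% and 0.0172 at 40%.
- E(N) = 40 − 10 × PET: 40 − 6.07 = 33.9, and 40 − 0.172 = 39.8.
- P(success) = P(X₄₀ ≥ 12) − P(X₃₀ ≤ 6 and X₄₀ ≥ 12): 0.0875 − 0.0013 = 0.0862 at 20%, and 0.9291 − 0.0022 = 0.9269 at 40%.

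**Because the look is only approximately at 30.** For one look anywhere from 28 to 32: type I error 0.085 to 0.087, power 92.5% to 92.8%, PET at 20% about 50% to 70%, E(N) at 20% 32.9 to 34.9, PET at 40% 1.1% to 2.5%, and E(N) at 40% 39.7 to 39.9.

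**The case against.** The stated figures are not miscalculated. Section 3.1.2.1.1 gives its condition, a start at 15 subjects, and refers to Table 3, whose rows run from 15 to 40. For that rule applied after each subject the numbers are right. That stands: the fault is an inconsistency, not an arithmetic error.

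A reader might infer that the trial lost its error control or that a reported result is affected. The documents do not support that. Section 2.4 plans no hypothesis test for this cohort, ORR is reported with an exact confidence interval and no p-value, and the look had already been made. Final decisions on stopping enrolment rested on the totality of the data (section 3.1.2.1). The type I error hardly moves, since with no look at all it would be 0.0875, and power rises.

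A reader might also call the early-termination sentence in section 2.4 false. It is a general comparison of methods, tied to the ability to look after each subject, and the text then turns separately to the single look in this study. It makes no claim about that look.

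Nor can the success cut-off be called missing. The shaded region of Table 3 does not show in the public text and may give both the boundary at 30 and the cut-off at 40. The protocol's stopping rules, to which section 2.3 refers, may do so too.

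None of this removes the mismatch: the section presents properties that the design in use does not have.

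**Conclusion.** The inconsistency is real, and its core needs no modelling: an expected sample size of 23.4 is impossible when the first chance to stop is at about 30 subjects. The figures that change materially concern early stopping. At a 20% response rate, PET is about 61% and not 89%, and expected enrolment is about 10 subjects higher (33.9 − 23.4 = 10.5). Type I error and power change little, and power in the favourable direction.

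Attributing the stated set to a look after every subject rests on the assumed 12/40 cut-off and Beta(0.2, 0.8) prior, which the agreement on all six figures supports. The single-look values rest on the cut-off but not on which of the tried priors is used, and they hold at exactly 30. Severity is moderate: the documented design properties are wrong for the schedule in use, while conduct and estimates are unaffected.

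**What to change.** - In section 3.1.2.1.1, label the six figures as those of the superseded design with monitoring after every subject from 15.
- Add the values for the look made, marked as holding at n = 30: stop if 6 or fewer responses, success if at least 12 of 40, type I error 0.086, power 92.7%, PET 60.7% at 20% and 1.7% at 40%, expected sample size 33.9 and 39.8. Say that for a look at 28 to 32, PET at 20% is about 50% to 70% and expected sample size at 20% about 33 to 35. If the exact number evaluable at the look is known, give the values for that number.
- The sponsor should first confirm the boundary, success cut-off and prior against Table 3 and the design file.
- In section 2.4, keep the general sentence and add that the early-termination advantage of frequent looks was not used in this study.

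The cost is SAP wording only. The stated type I error and early-stopping probability become less favourable; no analysis, data collection or display changes.

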3.1.2.2. Lymphoma Expansion Cohort

No interim analyses will be performed on the BCMA positive lymphomas cohort; though consideration would be given to closing the cohort should the enrolment be stopped in the MM cohort.

3.2. Administrative Interim Analyses

Additional administrative interim analysis may be performed to inform patient safety and efficacy of the drug as needed.

3.3. Final Analyses

The final planned primary analyses will be performed after the completion of the following sequential steps:

1. All participants have completed the study as defined in the protocol.
2. All required database cleaning activities have been completed and final database release (DBR) and database freeze (DBF) has been declared by Data Management.

A final analysis of the MM population can be done separately, before the NHL cohort completes, and will necessitate separate DBR/DBF activities.

4. ANALYSIS POPULATIONS

Population	Definition / Criteria	Analyses Evaluated
Screened	
 All participants who were screened for eligibility 	
 Study Population
Enrolled	
 All participants who passed screening and entered the study. Note screening failures (who never passed screening even if rescreened) and subjects screened but never enrolled into the study (Reserve, Not Used) are excluded from the Enrolled population as they did not enter the study. 	
 Study Population
All Treated	
 All eligible subjects who receive at least 1 dose of study treatment. An incorrect treatment schedule or drug administration or an early termination of treatment will not result in exclusion of subjects from this population. Sub-populations: 
 Part 1: all Part 1 subjects of All Treated population. Note, subjects in Part 1 are exclusively multiple myeloma patients. (2.5 mg/kg will be included in Part 1) Part 2 MM: all Part 2 MM subjects of All Treated population All Treated MM: comprise of subjects in Part 1 and Part 2 MM. Part 2 NHL: all Part 2 lymphoma subjects of All Treated population. 	
 Study Population Safety Efficacy
Evaluable (MM)	
 This population is a subset of the 'All Treated' population, who were initially treated at RP2D in the expansion cohort and have at least two post-baseline disease assessments or they have progressed or died or permanently discontinued treatment. 	
 futility analyses of MM Expansion cohort only
DLT Evaluable	
 All subjects fulfilling the 'All Treated' population criteria, and having met the following adequate exposure criteria: 
 For Schedule 1 (once every 3 weeks dosing) subjects received a complete infusion in cycle 1. For Schedule 2 (once weekly dosing for 3 consecutive weeks, 1 week rest) subjects receive three infusions, two of which must be complete infusions, in cycle 1. (as increases up to $\leq 30\%$ are implemented between cohorts, less than 2 complete infusions would result in a total dose closer to the previous dose investigated). (Schedule 2 was not explored in the study) Any subject in the "All Treated" population who experiences a DLT, as defined in Section 3.3.3 of the protocol will also be included in the DLT evaluable population regardless of exposure. 	
 Summary of DLT, for Part 1 only

Population	Definition / Criteria	Analyses Evaluated
Pharmacodynamic	
 The 'Pharmacodynamic (PD) Population' is defined as those subjects in the "All Treated" population from whom at least one PD sample was obtained, analyzed, and was measurable. 	
 PD
Pharmacokinetic (PK)	
 All subjects in the 'All Treated' population who had at least 1 non-missing PK assessment (Non-quantifiable [NQ] values will be considered as non-missing values). 	
 PK

Refer to [Appendix 12](#): List of Data Displays which details the population used for each display.

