2.2. Study Objective(s) and Endpoint(s)

Objectives	Endpoints
Primary Objectives	Primary Endpoints

 To determine safety, tolerability, maximum tolerated dose (MTD), and recommended phase (RP2) dose and schedule of GSK2857916 administered 	
 Adverse events (AE) and changes in clinical signs and laboratory parameters
Secondary Objectives	Secondary Endpoints

 To evaluate the pharmacokinetic (PK) profile of GSK2857916 and the breakdown product cys-mcMMAF after intravenous (IV) single and repeat dose administration in subjects with relapsed/refractory MM and BCMA expressing lymphomas 	
 GSK2857916 and cys-mcMMAF PK parameters following IV single and repeat dose administration during dose escalation as data permit (e.g., AUCs C_{max}, t_{max}, CL, V_{ss}, t_{1/2} [single dose], C_{max} and C_{trough} [repeat dose]). GSK2857916 population PK parameters in expansion cohorts at the RP2 dose (e.g. clearance (CL), volume of distribution (V_d)), and relevant covariates which may influence exposure (e.g. age, weight, or disease-related covariates e.g. BCMA expression)

 To assess anti-drug antibody (ADA) formation after IV single and repeat dose administration of GSK2857916 	
 ADA incidence and titers after single and repeat IV dosing of GSK2857916

 To explore the initial anti-tumor activity of GSK2857916 in subjects with relapsed/refractory MM and BCMA expressing lymphomas 	
 Clinical activity measured as Overall Response Rate (ORR) which is defined as follows: 
 For MM: the percentage of subjects achieving confirmed partial response or better (≥PR) In addition, the percentage of subjects with minimal response (MR) will be assessed for clinical benefit rate (CBR) (Appendix 1 of protocol) For Lymphomas: the percentage of subjects achieving PR or better (≥PR) (Appendix 2 of protocol)
Exploratory Objectives	Exploratory Endpoints

 To evaluate PD markers in MM after treatment with GSK2857916 	
 sBCMA levels, BCMA receptor occupancy and cell death markers in subjects with MM.

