4.1. Protocol Deviations

Important protocol deviations (including deviations related to study inclusion/exclusion criteria, conduct of the trial, patient management or patient assessment) will be summarised and listed.

Protocol deviations will be tracked by the study team throughout the conduct of the study in accordance with the Protocol Deviation Management Plan [08May2017, Version 6.0].

- Data will be reviewed prior to freezing the database to ensure all important deviations are captured and categorised on the protocol deviations dataset.
- This dataset will be the basis for the summaries and listings of protocol deviations.

A separate summary and listing of all inclusion/exclusion criteria deviations will also be provided. This summary will be based on data as recorded on the inclusion/exclusion page of the eCRF.

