7.2.1.3. Population of Interest

The secondary efficacy analyses will be based on the “All Treated” population, unless otherwise specified. Response data for multiple myeloma will be summarized by Study Part using the All Treated MM population and in subgroup: Prior anti-cancer therapy of interest as defined in Section 5.2.1.

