8. SAFETY ANALYSES

The safety analyses will be based on the “All Treated” population, unless otherwise specified.

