16.12.4. Study Population Tables

Study Population Tables					
No.	Population	IDSL / Example Shell	Title	Programming Notes	Deliverable [Priority]
Subject Disposition					
1.0010	All Treated	ES8	Summary of Subject Status and Reason for Study Withdrawal (Part 1)	Report for: Part 1, (Summarize: by ascending dose level, Total).	SAC [A]
1.0011	All Treated	ES8	Summary of Subject Status and Reason for Study Withdrawal (Part 2 MM)	Report for: Part 2 MM, (Summarize: only for 3.4 MM).	SAC [A]
1.0012	All Treated	ES8	Summary of Subject Status and Reason for Study Withdrawal (All Treated MM)	Report for: All Treated MM, (Summarize: Total).	SAC [A]
1.0013	All Treated	ES8	Summary of Subject Status and Reason for Study Withdrawal (Part 2 NHL)	Report for: Part 2 NHL, (Summarize: only for 3.4 NHL).	SAC
1.0020	All Treated	SD4	Summary of Treatment Status and Reasons for Discontinuation of Study Treatment (Part 1)	Report for: Part 1, (Summarize: by ascending dose level, Total).	SAC [A]
1.0021	All Treated	SD4	Summary of Treatment Status and Reasons for Discontinuation of Study Treatment (Part 2 MM)	Report for: Part 2 MM, (Summarize: only for 3.4 MM).	SAC [A]
1.0022	All Treated	SD4	Summary of Treatment Status and Reasons for Discontinuation of Study Treatment (All Treated MM)	Report for: All Treated MM, (Summarize: Total).	SAC [A]
1.0023	All Treated	SD4	Summary of Treatment Status and Reasons for Discontinuation of Study Treatment (Part 2 NHL)	Report for: Part 2 NHL, (Summarize: only for 3.4 NHL).	SAC
1.0030	Enrolled	NS1	Summary of Number of Participant by Country and Site ID (MM)	Include columns: No Treatment, Part 1, Part 2 MM, All Treated MM, Total column will be the subjects enrolled to MM cohort. Add a footnote: This summary is based on all subjects enrolled into multiple	SAC [A]

Study Population Tables					
No.	Population	IDSL / Example Shell	Title	Programming Notes	Deliverable [Priority]
				myeloma cohorts.	
1.0031	Enrolled	NS1	Summary of Number of Participant by Country and Site ID (NHL)	Include columns: No Treatment, Part 2 NHL, Total column will be the subjects enrolled to NHL cohort. Add a footnote: This summary is based on all subjects enrolled into lymphoma cohorts.	SAC
1.0050	All Treated	IE1	Summary of Inclusion/Exclusion Criteria Deviations (Part 1)	Report for: Part 1, (Summarize: by ascending dose level, Total).	SAC [A]

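### As written, All Treated admits only 'eligible' dosed subjects, an undefined condition that conflicts with the SAP's own displays and could drop dosed subjects from safety and response

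*SAP*

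**What the plan says.** SAP Section 4 sets two conditions for All Treated, eligibility and a dose: "All eligible subjects who receive at least 1 dose of study treatment". It then lists what does not remove a subject: "An incorrect treatment schedule or drug administration or an early termination of treatment will not result in exclusion of subjects from this population". Failure to meet an entry criterion is not on that list, and the SAP never defines 'eligible'.

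The population is used widely:

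- The primary endpoint in Section 2.2 is "Adverse events (AE) and changes in clinical signs and laboratory parameters", and Section 8 states: "The safety analyses will be based on the “All Treated” population, unless otherwise specified".
- Section 7.2.1.3 says of myeloma response: "The secondary efficacy analyses will be based on the “All Treated” population, unless otherwise specified". Section 7.2.2.3 does the same for lymphoma.
- DLT Evaluable is defined as "All subjects fulfilling the 'All Treated' population criteria, and having met the following adequate exposure criteria".
- The PK, PD and Evaluable (MM) populations, and the Part 1, Part 2 MM, All Treated MM and Part 2 NHL sub-populations, are also drawn from All Treated.

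Section 4.1 promises that "A separate summary and listing of all inclusion/exclusion criteria deviations will also be provided". Section 2 of the end-of-study RAP leaves the planned analyses and data handling unchanged, so the definition carries forward.

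**The concern.** A safety population normally rests on exposure alone, because an adverse event in a dosed subject is informative whether or not that subject should have been enrolled. Here a second condition has been added, and a programmer who applies it literally would remove dosed subjects who breached an entry criterion. Their adverse events, deaths, laboratory, ECG and ocular findings would leave the primary displays of a first-in-human study, and their responses would leave the ORR denominator.

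The deviation displays are built on the opposite premise. Whoever programs the study must follow either the definition or the display list, and the SAP does not say which prevails.

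**Working it through.** The SAP gives no figure to reproduce. The check is whether the definition and the displays can both hold.

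**1. Definition as a set.** All Treated = eligible AND dosed. If 'eligible' means meeting all inclusion/exclusion criteria, then All Treated AND not eligible = the empty set.

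**2. Deviation displays against the definition.** Section 16.12.4 specifies summary tables 1.0050 (Part 1), 1.0051 (Part 2 MM), 1.0052 (All Treated MM) and 1.0053 (Part 2 NHL) on All Treated. Section 16.12.13 does the same for listings 1.0050 and 1.0051. The end-of-study display list repeats table 1.0053 and both listings, again on All Treated. By step 1, each would contain zero subjects by construction. The important-deviation tables (1.0040 to 1.0043) would lose only their eligibility category.

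**3. Column layouts against the definition.** Tables 1.0030, 1.0031, 1.0060, 1.0061, 1.0290 and 1.0291 are run on Enrolled. Apart from totals, their columns are untreated and treated groups only. A subject who was dosed but fell outside All Treated would have no column. The layout works only if Enrolled = No Treatment + All Treated, which means every dosed enrolled subject is in All Treated.

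**4. Is there a way back in?** Safety and efficacy use All Treated by default, with exceptions allowed.

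- The named exceptions, DLT Evaluable for DLTs and Evaluable (MM) for futility, are subsets of All Treated.
- The rule that adds DLT cases regardless of exposure is itself confined to All Treated subjects.
- The listing of subjects excluded from any population (listings 1.0060 and 1.0061) is run on All Treated, so it could not show them.
- The exclusion summaries on Enrolled, chiefly table 1.0434, could count such a subject but would not report that subject's safety data.

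**5. Size per excluded subject.** The number of dosed subjects with an eligibility deviation is not given, so this is conditional arithmetic.

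- Single-subject run-in cohort (Section 3.1.1.1): 1/1 = 100% of that cohort's reported data.
- Cohort of three: 1/3 = 33%.
- Part 2 MM at its maximum of 40 (Section 2.3): 1/40 = 2.5% of the denominator.
- Effect on ORR, taking 16/40 = 40% (the alternative in Section 2.4) for illustration: dropping one non-responder gives 16/39 = 41.0%, and dropping one responder gives 15/39 = 38.5%. The shift is between +1.0 and -1.5 percentage points.

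**The case against.** The strongest reply is that 'eligible' is loose wording for having passed screening, which is how Section 4 describes the Enrolled population. On that reading, a subject accepted at screening and later found to breach a criterion stays in All Treated, the deviation tables fill normally, and nothing is lost. The displays in steps 2 and 3 support this as the sponsor's intention. That part stands: the documents do not show that any dosed subject is actually removed.

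Three stronger readings are tempting and are not supported.

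- A reader might infer that ineligible subjects will be excluded from the primary safety analysis. The SAP has no rule linking an inclusion/exclusion deviation to removal. The text permits exclusion when read literally but does not say it will happen.
- A reader might infer a post-hoc eligibility judgement that biases ORR. No adjudication step is described. Section 4.1 says only that deviations are tracked, reviewed before the database freeze, summarised and listed, with the eligibility summary taken from the eCRF page. Appendix 1 states that there is no per-protocol population.
- A reader might infer that dose finding was affected. Sections 3.1.1 and 3.1.1.3 base escalation on all available data and on the totality of the data, not on this reporting population.

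The reply does not remove the conflict. The SAP never equates 'eligible' with having passed screening, and it already has a separate population for that. If the intention is to keep everyone dosed, the word does no work and contradicts the displays.

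**Conclusion.** Wrong as written, and should be fixed. The definition of All Treated contradicts the displays planned on it. A literal application could omit a dosed subject with an eligibility deviation from the primary safety displays, from the DLT, PK and PD sets and from the ORR denominator.

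The conclusion rests on reading 'eligible' in its ordinary sense of meeting the entry criteria, since no other meaning is given. The realised effect is unknown and may be zero. It would be greatest in the smallest Part 1 cohorts and modest in Part 2 MM, at about 1 to 1.5 percentage points of ORR per excluded subject in the illustration above.

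**What to change.** In Section 4, define All Treated as every subject given one or more doses of study treatment, whether or not all eligibility criteria were met. Equivalently, delete 'eligible' and add eligibility deviations to the sentence listing what does not lead to exclusion. The sub-populations and the DLT Evaluable, Evaluable (MM), PK and PD populations inherit the correction, and the existing displays need no change.

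The cost is one edited definition. If the sponsor already intended to keep all dosed subjects, no result changes. The protocol is not at hand; if it carries the same restriction, the change should also be recorded in Table 1 of Section 2.1, which currently lists a revised PK population but nothing for All Treated.
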